7.2.2 Form

Tablet, oral, as hydrochloride: 150 mg, 300 mg

7.2.3 Storage and Stability

All pharmaceuticals will be stored at the Massachusetts General Hospital Oncology Clinical Trials Pharmacy (Yawkey-7).

7.2.4 Compatibility

N/A

7.2.5 Handling

Qualified personnel, familiar with procedures that minimize undue exposure to themselves and the environment, should undertake the preparation, handling, and safe disposal of the antimicrobial drug in a self-contained and protective environment.

7.2.6 Availability

All pharmaceuticals used in this study will be obtained from the in-patient pharmacy at MGH. Dispense of the bone labeling drugs will happen during the last clinical visit before the start of the radiotherapy. This will be approximately 3-4 weeks prior to the start of the labeling cycle. The total amount of pills for the labelset (24 tablets) will be divided over 2 bottles, each containing 12 pills. The bottles will be labeled 'Period 1' and 'Period 2', indicating one of the 3 day periods during which the pills are self-administered.

7.2.7 Preparation

All pharmaceuticals will be prepared at the Massachusetts General Hospital Clinical Trials Pharmacy. The bone labeling drugs will be divided in 2 bottles with 12 tablets per bottle. One bottle will contain the exact amount of pills that will be self-administered during one of the 3 day period. There will be 2 of these 3 day periods..

CONFIDENTIAL

This document is confidential. Do not disclose or use except as authorized.

7.2.8 *Administration*

Participants in the surgical arm will self-administer demeclocycline 150 mg PO QID (daily dose 600 mg) during 2 periods of 3 days with a 12 day interval, i.e. day 18, 17 and 16 and day 3, 2 and 1 day prior to the start of their scheduled radiotherapy. Demeclocycline will be administered 1 hour before or 2 hours after food or milk. Administer with adequate amounts of fluid to decrease the risk of esophageal irritation and ulceration. Patients will be instructed to take the bone labeling drugs no more than 3 consecutive days.

7.2.9 *Ordering*

All pharmaceuticals will be ordered through the Massachusetts General Hospital Clinical Trials Pharmacy. The designated pharmacist for this study is [name] at [contact]

7.2.10 *Accountability*

The investigator, or a responsible party designated by the investigator, must maintain a careful record of the inventory and disposition of the bone labeling drugs (investigational or free of charge) using the NCI Drug Accountability Record or another comparable drug accountability form.

7.2.11 *Destruction and Return*

At the end of the study, unused supplies of tetracycline and demeclocycline will be disposed of according to institutional policies. Destruction will be documented in the Drug Accountability Record Form.

8. CORRELATIVE/SPECIAL STUDIES

8.1 **Pharmacokinetic Studies**

N/A

8.2 **Pharmacodynamic Studies**

N/A

8.3 **Special Studies**

8.3.1 *Blood Draws*

We will follow the trends in serological markers over a 6 month period beginning prior to the first dose or radiation received by the patient. The study Schema outlines specific time points when we plan to draw

CONFIDENTIAL

This document is confidential. Do not disclose or use except as authorized.

the blood samples. After all studies have been performed we will label the samples with a code. The key to the code will connect the sample with the subjects health information. The key to the code will be kept in a password protected computer of the principal investigator. Samples will be stored at the BioBank and Research Laboratory Services for the Maine Medical Center Research Institute.

Figure 10

What is measured:

- N-Telopeptide (NTX)
- Serum tartrate-resistant acid phosphatase 5b (TRAP5b)
- Osteocalcin (OC)
- Type 1 procollagen N-terminal (P1NP).
- PTH
- Calcium as part of a standard metabolic panel
- Phosphate

8.3.2 *Quantitative CT Scans*

Patients in both arms of the study will undergo two QCT scans. First QCT will be done at Day 1, prior to initiation of radiation treatment. Patients in the Non-Surgical Arm will undergo a second QCT at six months after their first radiation treatment. In contrast, patients in the Surgical Arm will undergo their second QCT immediately prior to surgery, 10 weeks after the first scan. Once the spinal instrumentation is introduced during the surgery, it renders the analysis impossible due to artifact. Scans will be performed by the MGH Musculoskeletal Imaging Research Core (MIRC) under the direction of [name] (Radiology). We will use the QCT Pro protocol, detailed in Section 6.1.3 – Radiation Exposure Risks. Volumetric QCT of L1, L2 and S1 vertebrae will be obtained. Images will be saved in standard DICOM format and transferred to a PACS workstation for analysis.

What is measured:

- Trabecular bone mineral density (Tb. BMD)

8.3.3 *Bone Biopsies*

Bone biopsies will be performed on patients enrolled in the Surgical Arm of the study. Each patient will undergo two biopsies. At the time of each biopsy we plan to collect two bone samples. Figure 10 shows the location of the planned biopsy sites. The first biopsy (the control) will be taken from the iliac wing of the pelvis. This area lies outside of the radiated field, and will serve as a normal bone control. The second biopsy will be taken from the irradiated part of the sacrum. Bone biopsies will be evaluated for the end points of dynamic histomorphometry, and possible radiation-induced woven bone and bone mineralization abnormalities. Micro-CT will be performed on half of the bone samples prior to embedding to evaluate 3D trabecular microstructure. Biopsies that will be used for dynamic histomorphometry will be stored in 10% buffered formalin at room temperature in a dark space. We will send the biopsies to [name] at Columbia University for analysis. Transfers will be done in batches using FedEx. After all studies have been performed we will label the biopsies with a code. The key to the code will connect the biopsy with the subjects health information. The key to the code will be kept in a password protected computer of the principal investigator. Biopsies will be stored either at room

[figure not shown]
CONFIDENTIAL

This document is confidential. Do not disclose or use except as authorized.

temperature (embedded specimen) or frozen (fresh specimen) at the Endocrine Unit Research Laboratory of the Massachusetts General Hospital.

Figure 10 shows the location of two biopsy sites.

Figure 10: Location of the Planned Bone Biopsy Sites.

Biopsies will be done at the time of the scheduled tumor surgery. Sacral tumors are removed in stages. The first stage is done via anterior exposure, allowing access to the iliac crest. We will collect these samples first. Using a 7,5mm Rochester trephine two bone samples will be removed from the superior apex of the iliac wing in the midline (as defined as a point midway between the anterior superior and posterior superior iliac crests). In most cases, the biopsy site will be accessible through the incision made for the anterior approach. However, in those rare cases when the biopsy site is not accessible via the incision made as part of the standard of care, then a separate small incision (at most 3 cm long) will have to be made.

[figure not shown]
The second stage is done via posterior approach, providing access to the sacrum. We will collect the second biopsy samples during the second stage procedure. Using the same 7,5mm Rochester trephine, two bone samples will be removed from bone within one centimeter of the resection margin. To avoid unnecessary damage to healthy bone, we will attempt to collect the bone samples from the part of sacrum removed in surgery. After the tumor has been resected, it is normally brought to surgical pathology by the surgeon. There the specimen is examined by the pathologist. If there is enough normal bone remaining on the resected specimen, and the pathologist feels that using the normal bone will not interfere with his

CONFIDENTIAL

This document is confidential. Do not disclose or use except as authorized.

ability to assess the margin of resection, then the biopsy will be obtained from the surgical specimen rather than from bone remaining on the sacrum still attached to the patient's spine. Figure 11 illustrates the two possible sites of the sacral biopsy.

Figure 11: Location of Sacral Biopsy Site

Sacral Biopsy. This sagittal MRI image of the sacrum shows a large tumor at the caudal end. The entire sacrum was irradiated in this patient; the extent of the radiation field is approximated by the orange outline. During surgery, an axial cut through the middle of the sacrum was made to remove the tumor with negative margins. The portion of the sacrum removed is outlined in purple. For the purposes of our study, we would always try to take the bone samples from the portion of the sacrum to be discarded (A). In those cases when the fragment removed doesn't have enough healthy tissue for a biopsy, the samples will be collected from the portion of the sacrum that remains attached to the patient's spine (B). The approximate location of the biopsy site is marked with a trephine in A and B.

8.3.4 *Undecalcified Histology*

One control and one experimental sample from the biopsies will be embedded in plastic resin (MMA/dibutylphthalate) then split in half using a fine handsaw (0.3mm kerf). So as to not alter the mechanical properties of bone, one half will be scanned by micro-CT then processed for thin section histology. The other half will be sectioned at 1 mm intervals for quantitative back scatter electron imaging followed by nano indentation.

8.3.5 *Immunohistochemistry*

CONFIDENTIAL

This document is confidential. Do not disclose or use except as authorized.

Cellular content of bone can be evaluated by immunohistochemical staining methods. Osteoblasts will be counted on toluidine blue stained slides as blue/grey cuboidal cells in clusters at the bone surface. Osteoclasts will be counted on slides assayed for TRAP activity as TRAP-positive multinucleated cells.

What is measured:

- Osteoblast number (N.Ob/BPm, mm^{-1})
- Osteoblast surface (Ob. S/BS, %)
- Osteoclast number (N.Oc/BPm, mm^{-1})
- Osteoclast surface (Oc.S/BS, %)

8.3.6 *Micro-CT*

Undecalcified biopsies will be scanned with a micro-CT system (X-Tek HMXST 225 microfocus X-ray system, Nikon Metrology, Tring, UK).

What is measured:

- Bone volume fraction (BV/TV)
- Trabecular thickness (Tb.Th.)
- Trabecular separation (Tb.Sp.)
- Trabecular number (Tb.N.)
- Connectivity density (Conn.D)
- Structure model index (SMI)
- Trabecular bone pattern factor (TBPf)

8.3.7 *Nanoindentation*

Experimental design, data collection and analysis for nanoindentation will be done by our collaborator [name], who has the expert knowledge and experience with this technology. Bone samples for nanoindentation cannot be embedded in paraffin because it would alter the elastic properties. The portion of the biopsy specimen for nanoindentation will be collected and stored in a small amount of normal saline solution at 4°C. Bone can remain stored in this fashion for several weeks without compromising the quality of the data. Measurements will be done with a nanoindentation tester (Agilent G200 Nanoindenter, Santa Clara, CA) equipped with a diamond tip of Berkovich. The indentation will be performed with a load of 5 mN.

What is measured:

- Elastic modulus

8.3.8 *Tetracycline Quadruple Labeling*

We will use a quadruple labeling schedule, using two sets of double tetracycline labels which differ in color under fluorescent light (ie tetracycline and demeclocycline). Figure 12 shows the schedule for the administration of the bone labeling drug. This way we will be able to distinguish the first and second label

[figure not shown]
CONFIDENTIAL
This document is confidential. Do not disclose or use except as authorized.

set. This technique has the great advantage that the patient can serve as his or her own pretreatment control, eliminating problems caused by the large intersite variability in histomorphometric variables

What is measured:

- Mineral apposition rate
- Mineral formation rate
- Mineralization lag time

Figure 12: Tetracycline Administration Schedule

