9. STUDY CALENDAR

9.1.1 Non-Surgical Arm Study Calendar

Time point	Visit 1	Visit 2	Visit 3	Visit 4	Visit 5	Final visit
	Screening	Start RT Baseline	Halfway RT ~3.5 Weeks	End of RT ~7 Weeks	~3Months after RT	~6 Months after RT
Medical History	X					
Study Blood test		X	X	X	X	X
CT scan		X			X	
Pregnancy Test	X					

RT = radiotherapy

* Study visit are dependent on treatment events like start/end of pre- or post-op radiotherapy and surgery. Therefore treatment delay will result in delay of study visits.

CONFIDENTIAL

This document is confidential. Do not disclose or use except as authorized.

9.1.2 *Surgical Arm Study Calendar*

	Visit 1	Visit 2	Visit 3	Visit 4	Visit 5	Visit 6	Visit 7	Visit 8	Final Visit
	Before Surgery				Surgery Week		After post-op RT	Follow-Up	
	Screening	Start RT Baseline	End RT ~5.5 Weeks	3-5 days before surgery	Surgery stage 1	Surgery stage 2	End post-op RT	1 month after post-op RT	4 months after post-op RT
Medical History	X								
Eligibility blood test	X								
CT scan		X		X					
Study Blood test		X	X				X	X	X
Bone Biopsy					X	X			
Dispense drugs	X		X						
Pregnancy Test	X								

RT = radiotherapy

* Cycle 1 drugs will be taken between visit 1 and 2. Cycle 2 drugs will be taken between visit 3 and 4*
 Study visit are dependent on treatment events like start/end of pre- or post-op radiotherapy and surgery.
 Therefore treatment delay will result in delay of study visits.

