14.1.1 Primary Endpoint

- *Outcome of interest:* change in trabecular bone mineral density (Tb. BMD) measured by QCT of the lumbar spine at the start and at the end of radiation treatment

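### The primary endpoint is Tb. BMD change from start to end of radiation, but neither arm has a QCT at the end of radiation, and the non-surgical second scan has two conflicting dates

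*Combined protocol and SAP*

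**What the plan says.** Section 14.1.1 gives one primary endpoint: change in trabecular bone mineral density (Tb. BMD), "measured by QCT of the lumbar spine" and taken "at the start and at the end of radiation treatment". It does not distinguish the arms.

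Section 8.3.2 sets the scans. "Patients in both arms of the study will undergo two QCT scans", the first on Day 1 before radiation. For the second:

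- Surgical arm: "patients in the Surgical Arm will undergo their second QCT immediately prior to surgery, 10 weeks after the first scan". The reason given is "Once the spinal instrumentation is introduced during the surgery, it renders the analysis impossible due to artifact".
- Non-surgical arm: "Patients in the Non-Surgical Arm will undergo a second QCT at six months after their first radiation treatment".

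The calendars in section 9 both contain end-of-radiation visits, each with a study blood test and no CT:

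| Arm | End-of-radiation visit(s) | Second CT marked at |
|---|---|---|
| Surgical | Visit 3 (pre-operative course, about 5.5 weeks) and Visit 7 (post-operative course) | Visit 4, 3 to 5 days before surgery |
| Non-surgical | Visit 4 ("End of RT ~7 Weeks") | Visit 5, about 3 months after radiotherapy |

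On dose, section 5 gives surgical patients 50.4 Gy, a recovery of about 4 to 5 weeks, surgery, then 19.8 to 27 Gy. Non-surgical patients receive 72 to 77.4 Gy, over 7 to 8.5 weeks according to section 2.1. Section 2.1 also states the aim of studying doses above 70 Gy.

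The measured site varies too. Objective 1.2.1 names the sacrum, 14.1.1 the lumbar spine, and 8.3.2 says "Volumetric QCT of L1, L2 and S1 vertebrae will be obtained".

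**The concern.** With two scans per patient and neither second scan at the end of radiation, the primary endpoint has no data behind it as worded. Another time point has to stand in, and 14.1.1 does not say which.

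The consequences differ by arm. In the surgical arm (20 of 30 patients, called the main arm in 14.2) the only measurable change follows the pre-operative course. Without a clear definition it could be reported as the effect of the full course that section 2.1 sets out to study. In the non-surgical arm, 8.3.2 and the calendar cannot both be followed, so the follow-up interval is not fixed. If the arms are combined, the result mixes different prescribed doses and different intervals. Section 14.2 says the pilot is partly meant to supply numbers for later studies; a change with no stated time point or dose serves that purpose poorly.

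**Working it through.** **The plan's own figures.** Section 14.2 uses a change of 10, an SD of change of 15 (printed as mg/dL, read as mg/mL) and alpha 0.05. For a two-sided paired t-test the noncentrality is (10/15)·√n on n − 1 degrees of freedom. This gives power 0.942 at n = 30, 0.807 at n = 20 and 0.469 at n = 10, all as stated. The sample size arithmetic is not in dispute.

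**Surgical arm: timing.** Pre-operative radiation ends at about 5.5 weeks (section 9.1.2).

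- By 8.3.2 the scan is at 10 weeks, so the lag is 10 − 5.5 = 4.5 weeks.
- By section 5 and the calendar, the lag is the 4 to 5 week recovery less 3 to 5 days. Shortest: 4 − 5/7 = 3.3 weeks. Longest: 5 − 3/7 = 4.6 weeks. Adding 5.5 puts the scan at 8.8 to 10.1 weeks, which agrees with the stated 10.

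The two surgical dates are therefore consistent with each other. Neither is the end of the pre-operative course, and both precede the post-operative course.

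**Surgical arm: dose given by the last scan.**

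- With 19.8 Gy post-operatively: 50.4 / (50.4 + 19.8) = 50.4 / 70.2 = 72%.
- With 27 Gy: 50.4 / (50.4 + 27) = 50.4 / 77.4 = 65%.

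These are shares of the prescribed total, not of the dose at the bone measured.

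**Non-surgical arm: timing.** Taking a month as 4.35 weeks, 6 months is 26.1 weeks and 3 months is 13.0 weeks. Radiation lasts 7 to 8.5 weeks.

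- By 8.3.2: 26.1 weeks from first radiation, which is 26.1 − 8.5 = 17.6 to 26.1 − 7 = 19.1 weeks after radiation ends.
- By the calendar: 7 + 13.0 = 20.0 to 8.5 + 13.0 = 21.5 weeks from first radiation, 13.0 weeks after radiation ends.
- Conflict: (6 months − 3 months) − course length = 13.04 − 8.5 = 4.5 weeks to 13.04 − 7 = 6.0 weeks.

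**The arms compared.** The interval from baseline is about 10 weeks in one arm and 20.0 to 26.1 weeks in the other, a ratio of 20.0/10 = 2.0 to 26.1/10 = 2.6. Prescribed dose at the second scan is 50.4 Gy against 72 to 77.4 Gy.

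**Surgery.** Section 14.2 gives the non-surgical arm the role of controlling for confounding by surgery. Both surgical-arm scans are taken before surgery, so the QCT data contain no surgical effect to control for.

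**The case against.** The strongest reply is that the surgical-arm fault is loose wording. Each surgical patient has exactly one before/after difference, the calendar and 8.3.2 agree on when it is taken, and the timing is disclosed and explained by the instrumentation artifact. Section 14.2 words the comparison more loosely, as before and after radiation. The surgical calendar also labels the end of the pre-operative course as the end of radiotherapy. On this view the real conflict is confined to 10 patients and a few weeks, calendar times are approximate, and visits may move with treatment delays. Section 14.3 already stratifies by treatment type, and no bias or loss of power has been shown.

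Much of this stands. The pre-surgical scan is a reasoned choice and need not move, and the planned power is unaffected. But 14.1.1 is the defining section and it says the end of radiation. Even if that means the end of the pre-operative course, the scan is weeks later and at a different visit, and that reading does nothing for the non-surgical arm. Approximate visit times do not reconcile two dates counted from different starting points and at least 4.5 weeks apart. Stratifying by treatment does not amount to a written by-arm QCT analysis. That 14.1.1 cannot be computed as defined is literally true, even though a substitute difference exists.

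**Conclusion.** The concern holds and must be fixed. No scheduled scan in either arm matches the primary endpoint in 14.1.1. In 20 of 30 patients the last scan comes after 50.4 Gy prescribed (65% to 72% of the total), so QCT in that arm cannot show the effect of a course above 70 Gy. In the other 10 the plan leaves open whether the change is measured at about 20 to 21.5 weeks or about 26 weeks from first radiation.

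This rests on standard courses running as described in sections 2.1, 5 and 9. Treatment delays, or radiation given under another trial (which section 5 allows), would alter individual figures. The documents do not give the dose at the vertebrae measured, so the size of any distortion in the Tb. BMD change cannot be stated.

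**What to change.** Rewrite 14.1.1 by arm:

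- **Surgical:** change from baseline to the pre-surgical scan, described as following the pre-operative course only.
- **Non-surgical:** change from baseline to one named time after the full course. Section 8.3.2 and the calendar must be reconciled; the sponsor chooses the date.

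In the same rewrite:

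- Name the QCT site or sites and make 1.2.1, 14.1.1 and 8.3.2 agree.
- State that the QCT change is reported separately by arm, since prescribed dose and interval both differ.
- Limit the surgical-arm QCT conclusion to the pre-operative course.
- Note in 14.2 that both surgical-arm scans precede surgery, so QCT cannot inform the effect of surgery.
- As a secondary safeguard, make no QCT claim about doses above 70 Gy, in either arm, for a site whose dose is not documented.

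The cost is protocol wording and narrower QCT claims. It needs no extra scans or patients and no change in care.
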